4.3 Justification for dose

The roxadustat and rHuEPO doses used in this study are according to approved prescribing information available in the respective China Package Inserts.

Details on dose modifications are included in Section [6.6](#).

4.4 End of study definition

The end-of-study (EOS) is defined as the last expected visit/contact of the last patient undergoing the study.

A patient is considered to have completed the study when he/she has completed his/her last scheduled procedure shown in the SoA, [Table 1](#).

See Appendix [A 6](#) for guidelines for the dissemination of study results.

5 STUDY POPULATION

Prospective approval of CSP deviations to recruitment and enrollment criteria, also known as CSP waivers or exemptions, is not permitted.

Each patient should meet all of the inclusion criteria and none of the exclusion criteria for this study in order to be assigned/randomized to a study treatment. Under no circumstances can there be exceptions to this rule. Patients who do not meet the entry requirements are screen failures (Section [5.4](#)). Rescreening of patients is allowed as detailed in Section [5.4](#).

In this CSP, “enrolled” patients are defined as those who sign informed consent. “Screened” patients are defined as those who fulfil the inclusion/exclusion criteria and have not yet entered the Treatment Period. “Randomized” patients are defined as those who undergo randomization and receive a randomization number.

For procedures for withdrawal of incorrectly enrolled patients see Section 7.3.

5.1 Inclusion criteria

Patients are eligible to be included in the study only if all of the following inclusion criteria and none of the exclusion criteria apply:

Informed consent

- 1 Provision of signed and dated, written informed consent form (ICF) prior to any mandatory study specific procedures, sampling, and analyses.

The ICF process is described in Appendix A 3.

Age

- 2 Patient must be ≥ 18 years of age, at the time of signing the ICF.

Type of patient and disease characteristics

At Visit 1 prior to screening

Dialysis patients:

- 3 Patients receiving HD or PD for treatment of ESRD for at least 12 weeks. Patients treated with HD must have access consisting of an arteriovenous (AV) fistula, AV graft, or tunneled (permanent) catheter. Patients on PD must have a functioning PD catheter in place.
- 4 Hemodialysis patients should be on 3x/week dialysis with evidence of achievement of adequate dialysis as defined by $\text{stdKt/V} \geq 2.1$ in HD, and total (renal + PD) weekly $\text{Kt/V} \geq 1.7$ in PD documented twice during the 16 weeks preceding screening for the study.
- 5 Patients should be on a stable rHuEPO dose as defined by change in rHuEPO dose, not exceeding 20% within 4 weeks prior to screening.

Non-dialysis patients:

- 6 Patients with estimated glomerular filtration rate (eGFR) < 30 mL/minute/1.73 m², (calculated by central laboratory) corresponding to Stage 4 or Stage 5 CKD according to the Kidney Disease Outcomes Quality Initiative (KDOQI), and not receiving dialysis (Levey et al 2006).
- 7 Patients should either be on a stable dose of rHuEPO for 4 weeks before screening (defined as not exceeding 20% within 4 weeks prior to screening) or be rHuEPO-naïve (no ESA treatment for > 6 weeks before screening).

Dialysis and non-dialysis patients:

- 8 Patients agree not to take any new traditional Chinese medicine (TCM) and not to change, dose, schedule or brand of any TCM from beginning of the Screening Period through the end of the Follow-up Period.

At Visit 1 (screening)

- 9 Ferritin ≥ 50 ng/mL and transferrin saturation (TSAT) $\geq 15\%$ in non-dialysis patients (obtained from Visit 1, Screening Visit).
- 10 Ferritin ≥ 100 ng/mL and TSAT $\geq 20\%$ in dialysis patients (obtained from Visit 1, Screening Visit).

Weight

- 11 At Visit 1 (screening), dry body weight 45 to 100 kg (inclusive).

During the Screening Period

- 12 Dialysis patients must have a mean Hb level of ≥ 9 to ≤ 12 g/dL based on the mean of the 2 most recent central laboratory Hb values within 0.50 g/dL on 2 assays taken at least 7 days apart during the Screening Period.
- 13 Non-dialysis patients must have a mean Hb level of ≥ 9 to ≤ 12 g/dL for rHuEPO-user patients and ≥ 7 and ≤ 10 g/dL for rHuEPO-naïve patients, based on the mean of the 2 most recent central laboratory Hb values within 0.50 g/dL on 2 assays taken at least 7 days apart during the Screening Period.

At Visit 1 Screening

- 14 Serum folate level \geq lower limit of normal (LLN) (obtained from Visit 1, Screening Visit).
- 15 Serum vitamin B12 level \geq LLN (obtained from Visit 1, Screening Visit).
- 16 Alanine aminotransferase (ALT) or aspartate aminotransferase (AST) ≤ 3 x ULN and total bilirubin (TBL) ≤ 1.5 x ULN (obtained from Visit 1, Screening Visit).
- 17 Negative test results on the swab test to rule out active COVID-19 infection at the Screening Visit. If according to site procedures the test for COVID-19 infection cannot be performed at the first Screening Visit, the test should be performed as soon as possible thereafter but must be performed before the patient returns for the next study visit. Any participant who has had confirmed COVID-19 infection in the past, has fully recovered from symptoms at least 14 days prior to Screening, and has a negative swab test result for COVID-19 infection at Screening, may be included in the study.

Reproduction

- 18 At the start of the Screening Period, negative serum pregnancy test for female patients of childbearing potential.
- 19 Female patients of childbearing potential and male patients (non-surgically sterile ie, vasectomy) with a female partner of childbearing potential must, if not practicing complete sexual abstinence, agree to practice a dual method of contraception, for example, a combination of the following: (1) oral contraceptive, depot progesterone or intrauterine device; and (2) a barrier method (condom or diaphragm).

Contraceptive methods must be practiced upon being randomized to the study and until at least 7 days after the last dose of study treatment. Male patients must not donate or bank sperm during this same time period.

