1 PROTOCOL SUMMARY

1.1 Schedule of activities (SoA)

The schedule of activities (SoA) for the study is shown in [Table 1](#) below. The study consists of 3 periods: the Screening Period, Treatment Period and Follow-up Period.

Table 1 Schedule of activities

	Screening Period ^{a,b}	Treatment Period ^b			Discontinuation ^{b,c}	28-day Follow-up Period ^{c,d}	Details in CSP or Appendix section
Day	< -21 > -14 to 0	1	8 -1/+2 days	15 ± 2 days		43 ± 3 days	
Visit	1, 1a and 1b ^e	2	3	4		5	
Pre-screening telephone contact ^f							Section 4.1.1
Sign written ICF	X						Section 5 and Appendix A 3
Swab test for active COVID-19 infection ^g	X						Section 4.1.1
Eligibility criteria	X	X					Section 5
Demographics, medical and surgical history, and prior medication	X						Section 5
Hematology/hemostasis ^h	X ⁱ	X	X	X	X		Sections 5 and 8.2.1
HbA1C	X						Section 8.2.1
iPTH	X						Section 8.2.1
Physical examination, dry body weight ^j	X						Sections 5 and 8.2.2
Clinical chemistry ^k	X	X		X	X		Section 8.2.1
Urinalysis ^l	X	X		X	X		Section 8.2.1
Vital signs ^m	X	X	X	X	X		Sections 5 and 8.2.3
12-lead ECG	X						Section 8.2.4
Liver function tests ⁿ	X	X		X	X		Sections 5 and 8.2.1
Iron profile ^o	X	X		X	X		Sections 5 and 8.1
Hepcidin		X		X	X		Section 8.1
hs-CRP	X	X		X	X		Section 8.1

	Screening Period ^{a,b}	Treatment Period ^b			Discontinuation ^{b,c}	28-day Follow-up Period ^{c,d}	Details in CSP or Appendix section
Day	< -21 > -14 to 0	1	8 -1/+2 days	15 ± 2 days		43 ± 3 days	
Visit	1, 1a and 1b ^e	2	3	4		5	
Vitamin B12, folate	X						Sections 5 and 8.2.1
Terminate IV iron + TRIFERIC [®] in dialysate ^p	X						Section 5
Single dose of oral iron (12.5 mL [100 mg elemental iron]) administration		X ^q		X ^q	X		Section 6.1.3
Ferrokinetic study (T0 ^f , 1, 2, 3 hours)		X ^{q,r}		X ^{q,r}	X		Section 8.1
Concomitant medications	At every visit after Visit 1 and may be conducted by phone if not tied to a visit						Section 6.5
Routine safety measurements							
Adverse events	At every visit after Visit 1 and may be conducted by phone if not tied to a visit						Section 8.3
Serum pregnancy test ^s	X	X					Section 8.2.1
Study treatment administration							
Randomization ^t		X					Section 6.3 and Section 4.1.2
Study treatment dispensed ^u		X	X ^v				Section 6
Study treatment (rHuEPO and roxadustat) compliance			X	X	X		Section 6

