^a The Screening Period will be approximately 2-3 weeks long, but may be greater or lesser, to ascertain the Hb eligibility criteria with up to 3 Hb tests. To check Hb eligibility criteria, Hb levels must be assessed twice, at least 7 days apart, during the Screening Period; Hb levels may be assessed up to 3 times (Visits 1, 1a and 1b) during the Screening Period. The rHuEPO dose may be adjusted during the Screening Period for patients who were on rHuEPO before the Screening Period depending on the patient's Hb levels, at the discretion of the Investigator, in accordance with the rHuEPO China Package Insert. Results for Screening Period assessments for TSAT, ferritin, vitamin B12, serum folate, ALT, AST, hs-CRP and TBL must be available prior to starting the Treatment Period.

- b Each patient will be contacted within 24 h before a scheduled visit to confirm that he/she has no symptoms of COVID-19 infection and that he/she has had no contact with a known COVID-19 positive person within the past 14 days. If the patient reports symptoms or contact with a COVID-19-positive patient within the past 14 days, the Investigator may ask the patient to be tested for active COVID-19 infection (swab test to rule out active COVID-19 infection), or withdraw the patient from the study, as is most suitable for the patient's safety, at the Investigator's discretion. The study treatment and assessments may be continued as planned until the swab test results are available, at the discretion of the Investigator. Patients who test positive on the swab test must be withdrawn from the study. A patient who contacts the site at any time during the Treatment Period informing that he/she has symptoms suggestive of COVID-19 may be asked to get tested for active COVID-19 infection, or be withdrawn from the study for safety reasons, at the Investigator's discretion. Patients who test positive (for COVID-19) must be withdrawn from the study. Any study assessments planned on the days of site visits may be completed via a telephone call and/or a visit to the patient's home, as required, and if possible. The handling of patients and their blood or urine samples will be done using sterile techniques and observing precautions for infection control and prevention. Reasons for delayed site visits will be reported as protocol deviations. The actual dates when the visit-related assessments were completed will be recorded in the eCRFs.

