- m Vital signs will include tympanic temperature, systolic and diastolic BP, pulse rate and respiratory rate. Blood pressure should be measured prior to the hemodialysis procedure. For patients on PD, BP should be measured in the morning prior to the patient performing the first exchange of the day. Pulse rate and BP should be measured in triplicate after being comfortably at rest in a seated position with the back and feet supported (ie, by chair back and floor or platform, respectively) quietly for at least 5 minutes.
- n Alanine aminotransferase, AST, ALP, albumin, and TBL.
- o Serum iron, ferritin, TIBC, TSAT, transferrin, soluble transferrin receptor. On Days 1 and 15, blood samples for these assessments will be collected **before** time T0 (ie, **before administration of the single dose of oral iron**). Note that serum iron and TIBC are included in the ferrokinetic study and should not be taken as part of the iron profile as well on Days 1 and 15. There is no need to collect duplicate sample for serum iron and TIBC. The sample collected before the single dose of oral iron is administered can serve for the iron profile as well.
- p Intravenous iron and TRIFERIC® in dialysate should be stopped at the Screening Visit (ie, at Visit 1) and should not be taken after stopping, throughout the Screening and Treatment Periods, but can be started again after the Treatment Period.
- q Must be conducted prior to randomization at Day 1 and prior to the hemodialysis procedures at Days 1 and 15.
- r The blood samples for the ferrokinetic study (serum iron and TIBC) must be taken immediately **before** the single dose of oral iron is administered (ie, immediately before time T0), and then at T1, T2 and T3 after the single dose of oral iron (sample for serum iron only). The window of allowance for the ferrokinetic study blood sampling will be ±3 minutes.
- s Collect from female patients of childbearing potential only.
- t Results for Screening Period assessments for **ALT, AST and TBL must be available before randomization**. Randomization must occur after the ferrokinetic study has completed, ie, after collection of the T3 serum iron sample. Patients will be randomly assigned in 1:1 ratio to either roxadustat or rHuEPO. Study treatment to be administered after randomization at Day 1.

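### A Day 1 serum pregnancy test is scheduled, but no rule makes randomization or the same-day first dose wait for a negative result

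*Protocol*

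**What the plan says.** The eligibility rule is criterion 18 in Protocol Section 5.1: "At the start of the Screening Period, negative serum pregnancy test for female patients of childbearing potential". It names one test at one time.

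Table 1 in Section 1.1 has a row headed "Serum pregnancy test" with marks under Screening and under Day 1 (Visit 2), and none later. The only note on that row, footnote s, reads "Collect from female patients of childbearing potential only". It says who is tested, not what the result must be or when it must be known.

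Footnote t fixes the order of events on Day 1. First, "Randomization must occur after the ferrokinetic study has completed, ie, after collection of the T3 serum iron sample". Then, "Study treatment to be administered after randomization at Day 1". Section 4.1.1 likewise has the first dose given at the site on Day 1, after randomization.

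Serum hCG is listed in Table 4. Section 8.2.1 places Table 4 tests under the central laboratory manual.

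**The concern.** The Day 1 sample is taken at the right visit to prevent a first dose in pregnancy, but its result has no stated role in the decision to randomize or dose. A site could draw the sample, randomize, give the first dose and receive a positive result afterwards, without departing from any instruction.

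What is at stake is fetal exposure that the protocol itself regards as unacceptable: Section 8.4.2.1 wants treatment stopped at once when a patient becomes pregnant, and Section 7.1.2 lists pregnancy among the reasons for permanent discontinuation. Both act on a known pregnancy, so neither prevents a dose given before the result is known.

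**Working it through.** The protocol states no figure to reproduce here. The check sets the relevant rules side by side and adds some simple arithmetic.

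**Does any rule make dosing wait for the Day 1 result?**

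- Criterion 18: met by the test at the start of Screening. It does not mention Day 1.
- Table 1, eligibility row: marked at Screening and again on Day 1. Section 5 requires every entry criterion to be met for randomization, without exception. The recheck applies the criteria as worded, so the Screening result still satisfies criterion 18.
- Table 1 footnote s: defines who is tested and nothing more.
- Table 1 footnotes a and t, and Section 6.3: list results that must be in hand before the Treatment Period or randomization. None includes the pregnancy test.
- Sections 7.1.2 and 8.4.2.1: stop treatment once pregnancy is known.
- Section 8.4.2: foresees a pregnancy found before any dose, but only to exempt it from reporting.
- Exclusion 13 in Section 5.2: a general safety exclusion that an investigator could use for a known positive. It does not require waiting for the result.

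No rule does so.

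**How old can the qualifying result be on Day 1?**

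Section 1.2 gives total participation of 8 to 9 weeks, with 2 weeks of treatment and 4 weeks of follow-up:

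- 8 − 2 − 4 = 2 weeks (14 days)
- 9 − 2 − 4 = 3 weeks (21 days)

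This agrees with footnote a: "The Screening Period will be approximately 2-3 weeks long, but may be greater or lesser". The same footnote gives a floor of 7 days: "Hb levels must be assessed twice, at least 7 days apart, during the Screening Period". There is no firm maximum. A conception in that interval is what the Day 1 test would be expected to find, except one too recent to detect.

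**How many doses could precede a late result?**

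Section 6.1.2 spaces roxadustat doses by at least 2 days. If the Day 1 result arrives after the first dose but before the second, exposure is 1 dose. If it arrives before dosing, exposure is 0. The documents give no turnaround for hCG, so the range of 0 to 1 assumes that the result is known before the second dose. A slower result could add to it.

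**Is there time for a same-day result?**

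If blood for hCG is drawn with the sample taken just before the oral iron, the T3 sample follows 3 hours later, with a 3-minute window: 3 h − 3 min = 2 h 57 min at the least. Randomization cannot occur before then. A local test therefore has roughly 3 hours with no delay to the visit.

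**Does the protocol provide for a local result?**

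For hemoglobin it does: Section 8.2.1 sends Day 1 samples of rHuEPO patients to the local laboratory because the dose depends on them. Urine dipstick is also local. No such provision is stated for hCG.

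**The case against.** The best defence is that the intention is plain. Table 1 repeats both the eligibility check and the pregnancy test at the randomization visit, entry criteria admit no exceptions, and an investigator holding a positive result would not dose. That stands as far as it goes: a known positive would in practice be acted on. It does not cover a result still pending when the dose is given.

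A second objection is that the lists of results required before randomization prove little. They cover Screening assessments, where a Day 1 test would not belong, and they also omit the COVID-19 swab, which criterion 17 makes mandatory. This is correct. The point therefore rests on the wording of criterion 18 together with same-day dosing, not on those lists.

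Third, a late result is not demonstrated. Turnaround and handling may be set out in the central laboratory manual, which is not available here, and Section 8.2.1 does not say outright where hCG is run. This also stands, and it limits the claim to what the protocol permits.

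A reader might infer something stronger from criterion 19, which states "Contraceptive methods must be practiced upon being randomized to the study": that all of Screening is unprotected, that contraception should start earlier, and that a patient could be exposed for the whole Treatment Period. The documents do not support this. The Version 3.0 summary of changes says the contraceptive instruction was updated in line with the roxadustat package insert, which is not available to check, and the documents give no standard that the start date breaches. No study treatment is given before randomization, so the commitment covers the exposure period and at least 7 days after it. The Day 1 test re-examines the Screening interval. What would remain is a conception too recent to detect, which no pre-dose test can exclude.

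**Conclusion.** The point holds as a minor matter of patient safety. Eligibility depends on a pregnancy result that is nominally 14-21 days old at randomization. A fresh sample is scheduled on Day 1, but nothing requires its result before the first dose. As written, the protocol allows one dose in an undetected pregnancy that the Day 1 test would have revealed.

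This rests on two assumptions: that the Day 1 result can arrive after dosing, which the documents neither show nor rule out, and that it arrives before the second dose. Only women of childbearing potential are affected; their share of the 20-60 randomized patients is not given and is assumed small. Sample size, endpoints and analysis are untouched.

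**What to change.** Amend criterion 18 to require, in addition to the Screening test, a negative Day 1 serum pregnancy test with the result available before randomization. State the same condition in Table 1 footnotes s and t and in Section 6.3. Where the central laboratory cannot report the same day, allow the Day 1 test to be run locally, drawn with the pre-dose iron sample and read during the ferrokinetic study. Leave the contraception dates in criterion 19 as they are.

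The cost is amendment wording and, at some sites, a local hCG run for what is assumed to be a small number of women. No visit is added, and randomization need not be delayed if the local result is back within the roughly 3 hours that must already pass.

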5.2 Exclusion criteria

Medical conditions

- 1 New York Heart Association Class III or IV congestive heart failure (CHF) at screening.
- 2 Acute coronary syndrome, stroke, seizure or a thrombotic/thromboembolic event (eg, deep vein thrombosis or pulmonary embolism) within 12 weeks prior to randomization.
- 3 History of severe, chronic, end-stage, or uncontrolled autoimmune liver disease with ALT > 3 x ULN, or AST > 3 × ULN, or total bilirubin > 1.5 × ULN.
- 4 Known hereditary hematologic disease such as thalassemia, sickle cell anemia, a history of pure red-cell aplasia or other known causes for anemia other than CKD.
- 5 Known and untreated retinal vein occlusion or known and untreated proliferative diabetic retinopathy (risk for retinal vein thrombosis).
- 6 Systolic blood pressure (BP) ≥ 160 mm Hg or diastolic BP ≥ 95 mm Hg (confirmed by repeated measurement), within 2 weeks prior to randomization. Patients may be rescreened once BP is controlled.
- 7 History of prostate cancer, breast cancer, renal cell carcinoma or any other malignancy, except the following: cancers determined to be cured or in remission for ≥ 5 years; curatively resected basal cell or squamous cell skin cancers, cervical cancer in situ, or resected colonic polyps.
- 8 Chronic inflammatory diseases such as rheumatoid arthritis, systemic lupus erythematosus (SLE), ankylosing spondylitis, psoriatic arthritis or active inflammatory bowel disease that is determined to be the principal cause of anemia.
- 9 Known hemosiderosis, hemochromatosis or hypercoagulable condition.
- 10 Any prior organ transplant or a scheduled organ transplantation date.
- 11 Any current condition leading to active significant blood loss.
- 12 Known allergy to the study treatment or any of its ingredients.

- 13 Any medical condition, including active, clinically significant infection, that in the opinion of the Investigator or Sponsor may pose a safety risk to a patient in this study, which may confound safety or efficacy assessment or may interfere with study participation.
- 14 Intolerance of oral iron in the past as defined by stomach upset, nausea, vomiting, or diarrhea.
- 15 Active GI bleed.
- 16 Hospitalizations within the 12 weeks preceding study randomization for GI bleeding or CHF.
- 17 Life expectancy <6 months.
- 18 Patients who are likely to be initiated on dialysis within the next 3 months per Investigator's assessment at the time of screening.
- 19 Previous bowel resection.
- 20 Coeliac disease.
- 21 Gastroenteritis in the 4 weeks prior to randomization.
- 22 Cognitive disabilities, physical or psychiatric disease that in the opinion of the Investigator/clinician influence the patient's adherence and successful completion of the study.

Prior/concomitant therapy

- 23 Any treatment with roxadustat or a HIF-PHI.
- 24 Any RBC transfusion within 6 weeks prior to the first Screening Visit, or during the Screening Period.
- 25 Has received another new chemical entity (defined as a compound which has not been approved for marketing) within the 12 weeks prior to Screening Visit.
- 26 Exposure to IV iron or use of TRIFERIC® in dialysate during the Screening Period (ie, 2 weeks before randomization [Day 1]).
- 27 Exposure to iron-chelating agent (eg, deferoxamine/desferrioxamine, deferiprone or deferaxirox therapy) within the 6 weeks prior to the first Screening Visit.

Prior/concurrent clinical study experience

- 28 Participation in any other clinical study that included drug treatment within at least 4 weeks of screening. (Note: patients consented and screened, but not randomized in this study or a previous study are not excluded).

Other exclusions

- 29 Involvement in the planning and/or conduct of the study (applies to AstraZeneca and FibroGen staff and/or staff at the study site).

- 30 Patient non-adherence to medications or missing > 1 dialysis treatments/month per the Investigator's knowledge.
- 31 Previous randomization in the present study.
- 32 History of alcohol or drug abuse within 2 years prior to randomization.

